Hypothesis 2. Recipients of supported SCIT are expected to demonstrate performance gains on measures of social cognition, perceived social support, social competence, social comfort, and work performance post-intervention.

Specific Aim 3: This study will assess durability of intervention-induced change.

Hypothesis 3: Recipients of supported SCIT are expected to sustain gains in social cognitive and functional domains during a 3-month follow-up period.

Methods:

Study Design. An open-trial pilot study will be conducted in which participants attend 12 weeks of supported SCIT.

Participant Inclusion/Exclusion Criteria. Participants will be individuals, ages 18-70, with a DSM-5 diagnosis of schizophrenia, schizoaffective disorder, or bipolar disorder who are engaged in work activity. In addition, participants must be clinically stable, defined as no psychiatric hospitalizations and no changes in antipsychotic or mood stabilizing medication in the 4 weeks prior to study enrollment, and participants must be able to participate appropriately in a group-based activity, as judged by no recent history of disruptive behavior in groups and no history of unprovoked aggression toward others. Participants will be excluded if they have met criteria for substance abuse in the last month or substance dependence in the last 6 months, if they are not fluent enough in English to understand testing procedures, if they have premorbid IQ less than 70, or if they do not have the capacity to give informed consent.

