participant is unable to maintain attention to the description of the consent form long enough to perceive the individual basic points in the consent form; 3) the potential participant cannot ask questions or respond sufficiently to indicate agreement due to catatonia; or 4) the potential participant expresses delusions related to the research protocol that significantly distort his or her basic understanding of the research. In contrast, some indicators that the potential participant can provide meaningful consent will include: 1) ability to pay attention well enough to read the form or have it read and described to him/her; 2) ability to paraphrase the basic points in the consent form; and 3) ability to ask reasonable questions about the research and associated treatment conditions.

Study Intervention. The intervention will consist of one 2-hour, small group training session and 30-minutes of individualized supported practice of skills with a treatment facilitator weekly. [name] and bachelor and master's level assistants will offer the intervention. The Social Cognitive Intervention Training (SCIT) will be described as a relationship skills class. The class will consist of a combination of lecture, demonstrations, and role-play activities. Participants will learn skills to facilitate emotion recognition. They will also learn strategies to assist with perspective taking and assessing the accuracy of attributions about social situations.

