Assessment. See Table 1 for all assessment measures. Participant diagnosis will be established with a SCID diagnostic interview. In addition, to establish eligibility, structured interviews will be conducted to obtain participant demographics, medical, and psychiatric history. In addition, the Wechsler Test of Adult Reading will be administered to obtain an estimate of pre-morbid IQ. Baseline, post-intervention (3-month), and follow up (6-month) assessments will measure social cognitive training targets, functional outcomes, and potentially confounding variables such as symptom severity with instruments previously used with this patient population. Social cognitive domains will be assessed with the Bell-Lysaker Emotion Recognition Task, the Ambiguous Intentions and Hostility Scale, the Facial Emotion Identification Test, and The Awareness of Social Inference Task. Social competence, community functioning, perceived social support at work, and social comfort at work, will be assessed with the Social Skills Performance Assessment, the Mentoring and Communication Support Scale, the First Episode Social Functioning Scale, the Vocational Efficacy in Trauma Survivors Scale, and the Mentoring and Communication Support Scale. Potential confounds, symptom severity and outside treatment hours, will be assessed with the Brief Psychiatric Rating Scale and the treatment update interview.

Statistical Analysis: Descriptive statistics, including means, standard deviations, and measures of frequency will be used to describe the sample as well as uptake and engagement in treatment. Repeated measure ANOVAs and paired sample t-tests will be used to test for the effects of Time on social cognitive and functional outcome variables. Magnitude of within group change with treatment will be measured with Cohen's d.

References

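### Any retest effect on the repeated social cognition tasks would enter the Time effect and Cohen's d in full, yet Aims 2 and 3 attribute the change to the intervention

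*Combined protocol and SAP*

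**What the plan says.** Under Study Design, the trial has one arm: "An open-trial pilot study will be conducted in which participants attend 12 weeks of supported SCIT". No comparator is described.

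Under Assessment, the schedule is: "Baseline, post-intervention (3-month), and follow up (6-month) assessments will measure social cognitive training targets, functional outcomes, and potentially confounding variables such as symptom severity". Four instruments cover the training targets. The Awareness of Social Inference Task is the last of them, and the first three are named here: "Social cognitive domains will be assessed with the Bell-Lysaker Emotion Recognition Task, the Ambiguous Intentions and Hostility Scale, the Facial Emotion Identification Test". The Social Skills Performance Assessment is among the functional measures. The paragraph refers to Table 1 for all measures, but that table is not in the text available for review.

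Under Study Intervention, the class teaches what several of these tasks measure: "Participants will learn skills to facilitate emotion recognition". Perspective taking and the accuracy of attributions are also taught.

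The confounds that the plan intends to measure are two: "Potential confounds, symptom severity and outside treatment hours, will be assessed with the Brief Psychiatric Rating Scale and the treatment update interview". Retest is not among them.

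Under Statistical Analysis: "Repeated measure ANOVAs and paired sample t-tests will be used to test for the effects of Time on social cognitive and functional outcome variables". The effect measure is described thus: "Magnitude of within group change with treatment will be measured with Cohen's d". The standardiser of d is not stated.

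Specific Aim 2 speaks of the *impact* of supported SCIT, and Specific Aim 3 calls the change *intervention-induced*.

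**The concern.** A participant who meets an emotion-recognition, social-inference or social-skills performance task for the second or third time may score differently because the items or the format are familiar. With one arm, such a shift cannot be told apart from a training effect. It arises from the assessment schedule, so it could occur in patients whose symptoms and outside treatment never change. Recording those two confounds therefore does not remove it.

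If the shift is towards better scores, it favours Hypothesis 2 on the tests closest to what the class teaches. If it also lasts, or is renewed by the third exposure, it could look like the durability sought in Hypothesis 3. A later trial planned from the pilot's d would inherit the same component.

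**Working it through.** **Plan's own figure.** There is none to reproduce. The documents give no sample size, significance level, expected effect, SD or retest correlation for these outcomes.

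**How retest enters the estimate.** In a single arm, expected change = training effect + retest effect + other effects of time. The paired t-test, the repeated-measures ANOVA and the within-group d all work on this sum. The retest term passes through one for one, whatever its size or sign.

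**Illustration.** All inputs are assumptions:
- training effect zero;
- two-sided alpha 0.05, so 0.025 in the direction of gain;
- retest shift towards gain, expressed as dz, the mean change divided by the SD of change;
- n of 20, 30 or 40 participants with paired data.

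The chance of a significant gain is P(T > t(0.975, n−1)), where T is non-central t with n−1 degrees of freedom and non-centrality dz × √n. For n=20 and dz=0.2, the critical value is 2.093 and the non-centrality is 0.2 × √20 = 0.894, which gives 0.133.

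| dz | n=20 | n=30 | n=40 |
|---|---|---|---|
| 0 | 0.025 | 0.025 | 0.025 |
| 0.05 | 0.040 | 0.045 | 0.049 |
| 0.1 | 0.062 | 0.076 | 0.090 |
| 0.2 | 0.133 | 0.184 | 0.234 |
| 0.3 | 0.246 | 0.355 | 0.456 |
| 0.4 | 0.397 | 0.563 | 0.694 |

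**Sensitivity to the scale of the shift.** If the shift d is instead in units of the SD at one visit, with retest correlation r and equal SDs, then dz = d / √(2(1−r)). At r=0.5 the divisor is 1 and the table is unchanged. At r=0.7 the divisor is √0.6 = 0.775, and shifts of 0.1, 0.2, 0.3 and 0.4 SD give 0.079, 0.194, 0.376 and 0.592 at n=20, and 0.101, 0.277, 0.536 and 0.780 at n=30.

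**Inflation of d.** If d is standardised by the SD of change, a retest shift of dz adds exactly dz. If it is standardised by the baseline SD, the shift adds dz × √(2(1−r)). At r=0.7, dz of 0.1 to 0.4 adds 0.1 × 0.775 = 0.08 to 0.4 × 0.775 = 0.31. At r=0.5 the two versions coincide.

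**Check that the missing comparison is the cause.** Take a retest gain of 0.3 SD and r=0.7. In a simulation with an untrained arm tested on the same schedule, the between-arm test of change showed a false gain in 2.5% of runs at 10, 20 and 30 per arm. The planned single-arm test under the same assumptions does so with probability 0.19 at n=10, 0.38 at n=20 and 0.54 at n=30.

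**The case against.** The strongest reply is that the study is openly an uncontrolled pilot. Its first aim is feasibility, its effect measure is labelled within-group change, and retest is only one of several components of any pre-post difference. That stands for Aim 1, for which a single arm is suitable. It does not cover Aims 2 and 3, which put directional hypotheses to significance tests and use causal wording.

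A reader might infer more than the documents support:
- *That the plan uses no alternate forms.* The available text is silent, and Table 1 could list versions. Only 'none described' is justified.
- *That retest moves scores in the hypothesised direction and lasts to 6 months.* The documents hold no retest data for these tasks over such intervals. Direction, size and persistence are all open, and at a shift of 0.05 the chance at n=20 is only 0.04.
- *That d is inflated by exactly the assumed shift.* This depends on a standardiser that the plan does not name.
- *That every listed instrument is equally exposed.* The Ambiguous Intentions and Hostility Scale is titled a scale, and nothing in the documents shows that its items can be learned. The point is weaker there.

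**Conclusion.** The concern holds in a limited form. The design and analysis contain no described means of separating a retest effect from training, and neither named confound would do so. That conclusion needs no assumption about size. The consequence, if retest shifts scores towards gain by 0.1 to 0.4 SD of change and training does nothing, is a chance of a significant gain per test of about 0.06 to 0.40 at n=20 and 0.08 to 0.56 at n=30, against 0.025. Sample size, alpha and shift are all assumed, so these figures show what could happen and do not estimate what will. The documents do not support saying that the pilot's gains would be mostly retest. They support saying that the plan cannot tell, while Aims 2 and 3 are worded as if it could.

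**What to change.** 1. In the Assessment paragraph, state which version of each task is used. Where a task has established equivalent forms, give different forms across visits, counterbalance their order across participants, and include form in the analysis. With three visits and only two forms, one form must recur.
2. For single-form tasks, report d as uncontrolled within-group change that includes any retest effect. State the standardiser of d for all outcomes.
3. Replace *impact* in Aim 2 and *intervention-induced* in Aim 3 with wording that does not credit the change to training alone.

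The cost is a rotation schedule and a few sentences. The downside is slight noise from differences in difficulty between forms. Rotation reduces carry-over of items but does not remove general familiarity with testing, so the rewording is needed even where forms exist. If rotation is no longer practicable, items 2 and 3 can still be adopted.

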Results of recent studies suggest that social cognitive abilities are modifiable in both schizophrenia⁽¹²⁾ and bipolar disorder⁽¹³⁾. Presently, the most established intervention is Social Cognitive Intervention Training (SCIT), a 12-week group intervention in which participants learn strategies to enhance emotion recognition and to assess the accuracy of their interpretation of social interactions⁽¹⁴⁾. SCIT's ultimate goal is for training to transfer beyond the social cognitive training targets to more distal outcomes such as enhanced role functioning. The first full scale clinical trial of SCIT's efficacy found that the impact of training generalized beyond social cognitive performance and resulted in increased skillfulness in social interactions⁽¹⁵⁾.

To enhance transfer of training gains to functional outcomes, two pilot studies have paired participants with a social mentor to facilitate completion of homework and to ensure that skills are practiced outside of treatment (supported SCIT). Both studies reported improvements not only in social cognition but also in social relatedness⁽¹⁶⁾ and community functioning⁽¹⁷⁾. The proposed study will extend this work by being the first to examine the impact of supported SCIT on work role functioning. When other types of skills training have been paired with work, a synergistic effect has been noted, with greater^(18, 19) and more sustained⁽²⁰⁾ treatment gains observed, presumably because work offered opportunities to practice skills.

Specific Aim 1: This study will assess the feasibility of providing supported SCIT to individuals with serious mental illness who are engaged in work activity or school (i.e., competitive employment, hospital based compensated work therapy placement, volunteer work, school). One 2-hour group-based skills training sessions will be offered weekly. The group training will be supplemented with individual sessions with a group co-facilitator to complete homework tailored to the work setting.

Hypothesis 1. Supported SCIT will be completed by 75% of enrolled veterans, a rate comparable to non-supported SCIT offered to non-veterans⁽²¹⁾. Completion will be defined as attendance at 80% or more of group and individual sessions.

Specific Aim 2: This study will assess the impact of supported SCIT on social cognitive intervention targets as well as functional outcomes.

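### Aims 2 and 3 have no analysis set or missing-visit rule, so the ANOVA and paired t-tests can rest on different people; one mixed model on all enrolled participants would settle this

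*Combined protocol and SAP*

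**What the plan says.** All references are to the combined protocol and SAP.

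- **Study Design:** a single-arm study. "An open-trial pilot study will be conducted in which participants attend 12 weeks of supported SCIT".
- **Assessment:** three time points. "Baseline, post-intervention (3-month), and follow up (6-month) assessments will measure social cognitive training targets", as well as functional outcomes and possible confounders.
- **Statistical Analysis:** beyond descriptive statistics, two sentences cover Aims 2 and 3. The first names the tests: "Repeated measure ANOVAs and paired sample t-tests will be used to test for the effects of Time on social cognitive and functional outcome variables". The second names Cohen's d as the effect size: "Magnitude of within group change with treatment will be measured with" that statistic. No analysis set, missing-visit rule or standardiser is given.
- **Hypothesis 1** has a clear denominator: "Supported SCIT will be completed by 75% of enrolled veterans". It also has a clear threshold: "Completion will be defined as attendance at 80% or more of group and individual sessions".
- **Hypotheses 2 and 3** use a different, undefined population: "Recipients of supported SCIT are expected to demonstrate performance gains on measures of social cognition", and "Recipients of supported SCIT are expected to sustain gains in social cognitive and functional domains during a 3-month follow-up period".

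The available text does not say whether people who stop attending will be assessed at 3 and 6 months. Table 1 (assessment measures) and the consent pages are not in the published text, so they cannot be checked.

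**The concern.** With no control arm, within-person change is the only evidence for Aims 2 and 3. Three things are left open.

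1. **Who is analysed.** Recipients could mean everyone enrolled, everyone who attended at least once, or those who reached 80% attendance. Hypothesis 1 itself expects about a quarter of those enrolled to fall below that threshold.
2. **What happens to a missed visit.** A classical repeated-measures ANOVA needs all three visits and a paired t-test needs two. One outcome can therefore give different gains depending on which named test is reported.
3. **Whether people who stop are assessed.** Treatment lasts 12 weeks and the first follow-up is at 3 months, so someone who stops during treatment may miss both follow-ups.

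Hypothesis 3 suffers most. A reader could not tell a sustained gain from a change in who came back. Aim 1 (feasibility) is unaffected.

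**Working it through.** The plan states no sample size, SD, effect size or missed-visit rate, so it has no figure of its own to reproduce. Every input below is an assumption, except the three visits and the two named tests.

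**Step 1. How the subsets differ.** Let N be enrolled, r3 the share assessed at 3 months, r6 the share of those also assessed at 6 months, and b the share of those missed at 3 months who return at 6.

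- Baseline-to-3-month pairs: N × r3
- ANOVA set: N × r3 × r6
- Baseline-to-6-month pairs: N × r3 × r6 + N × (1 − r3) × b

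With N = 30, r3 = 0.75, r6 = 0.8 and b = 0.2: 30 × 0.75 = 22.5; 22.5 × 0.8 = 18; 18 + 7.5 × 0.2 = 19.5. That is three different sets. If b = 0 (nobody returns after a missed visit), the 6-month pairs equal the ANOVA set and only the 3-month set differs.

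**Step 2. Bias.** Large-sample simulation with unit SDs, correlation r = 0.7 between visits, and true gains of 0.40 SD at 3 months and 0.30 SD at 6. The odds of being missing rise 1.65-fold (moderate) or 2.7-fold (strong) per SD smaller baseline-to-3-month gain. In pattern (a) only the 6-month visit is missed; in pattern (b) both follow-ups are missed. Gains at 3 / 6 months with 25% missing:

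| Estimate | Moderate | Strong |
|---|---|---|
| Truth | 0.40 / 0.30 | 0.40 / 0.30 |
| Complete cases, (a) or (b) | 0.493 / 0.346 | 0.565 / 0.383 |
| Mixed model, (a) | 0.400 / 0.300 | 0.400 / 0.301 |
| Mixed model, (b) | 0.480 / 0.332 | 0.543 / 0.360 |
| Mixed model, (b), random half of the missing assessed | 0.434 / 0.314 | 0.461 / 0.326 |

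- Complete-case bias at 3 months: 0.493 − 0.40 = 0.093 and 0.565 − 0.40 = 0.165. At 10% missing it is 0.04-0.07, and at 5% it is 0.02-0.04.
- In (b) the model alone removes (0.493 − 0.480)/0.093 = 14% of the moderate 3-month bias. Assessing half of those people and using the model removes (0.493 − 0.434)/0.093 = 63%.
- If good responders are the ones missing both follow-ups (25%), complete cases show 0.24-0.31 and 0.22-0.25, so the bias is downward. If missingness is unrelated to outcome, there is none.

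**Step 3. Durability in pattern (a).** The true 3-to-6-month loss is 0.40 − 0.30 = 0.10.

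- Each paired t-test on its own subset: 0.400 − 0.346 = 0.054, or 0.400 − 0.383 = 0.017. Gains look better sustained than they are.
- Complete cases throughout: 0.493 − 0.346 = 0.147, or 0.565 − 0.383 = 0.182. Gains look worse sustained than they are.
- Mixed model: 0.10.

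**Step 4. Scale.** The SE of a mean change is √(2(1 − 0.7)/n). With 25% missing from 24 or 40 enrolled, 18 or 30 are analysed, and the SE is √(0.6/18) = 0.183 or √(0.6/30) = 0.141. The moderate bias is 0.093/0.183 = 0.51 to 0.093/0.141 = 0.66 SE; the strong bias is 0.165/0.183 = 0.90 to 0.165/0.141 = 1.17 SE. At 10% missing, even the largest bias is 0.07/√(0.6/36) = 0.54 SE with 40 enrolled.

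**Step 5. Type I error of the Time test with no true change** (simulated, 24 and 40 enrolled). The complete-case ANOVA rejects in about 5-7% of trials at 10% missing. At 25% missing it rejects in about 6.5-17%, the top value needing strong dependence and 40 enrolled. Over both rates the mixed model with Kenward-Roger degrees of freedom rejects in 4.8-6.0% in pattern (a) and 4.9-13.6% in (b).

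**Step 6. Cohen's d.** With r = 0.7, a gain of 0.40 baseline SDs is 0.40/√0.6 = 0.52 SDs of change. That gap of 0.12 exceeds every 10%-missing bias above, so the standardiser has to be named.

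**The case against.** Several points on the other side stand.

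- **A reader might infer that the plan excludes people who drop out.** The documents do not support that. The Assessment section attaches no attendance condition to the three visits, and Participant Recruitment says the consent form will describe the procedures in detail. One can say only that the available text is silent.
- **A reader might take the 25% implied by Hypothesis 1 as the missed-visit rate.** It is the share expected below 80% attendance; such people may still be assessed. The 25% results are one scenario, and at 5-10% the bias is much smaller.
- **A reader might conclude that the two tests must disagree, or that gains will be overstated.** Neither follows. The subsets reflect the usual behaviour of these methods, not a statement in the plan. They coincide if no visit is missed or if the same people miss both follow-ups; in that second case all the named tests share the same bias. The bias can also be zero or downward.
- **The mixed model is no cure for pattern (b).** This is correct, and it is why seeking the assessments matters more there than the choice of model.
- **This is an uncontrolled pilot**, so practice and the passage of time already confound within-person change. That limits the weight of the point but does not remove it: the remedy is cheap, and Hypothesis 3 cannot be read without knowing who is in each contrast.

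**Conclusion.** The point holds as an inexpensive improvement that should be made, not as a demonstrated bias. From the text alone, Aims 2 and 3 have no analysis set, no missing-visit rule and an undefined population, and the named tests in their usual form can use different people for post-treatment gain and for durability.

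The size cannot be known from the documents. Under the assumptions shown, with poor responders more often missing, the 3-month complete-case bias runs from 0.02-0.04 SD at 5% missing to 0.09-0.17 at 25%. It is around one standard error only at 25% with strong dependence. Type I error is near nominal at 10% missing and clearly inflated only at 25% with strong dependence. One mixed model removes the bias when only the 6-month visit is missed for reasons reflected in observed scores; when both follow-ups are missed it removes little.

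**What to change.** In Statistical Analysis:

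1. Define the analysis set for Aims 2 and 3 as all enrolled participants with a baseline score. Report completers (80% attendance) as secondary.
2. Replace the ANOVA and t-tests for each outcome with one REML linear mixed model: categorical visit (baseline, 3, 6 months), unstructured within-person covariance, Kenward-Roger degrees of freedom.
3. From that model report the baseline-to-3-month, baseline-to-6-month and, for Hypothesis 3, 3-to-6-month contrasts with 95% CIs.
4. Base Cohen's d on those contrasts with one stated standardiser, for example the baseline SD.
5. Acknowledge that the model corrects for missing 6-month visits explained by observed scores, but only partly for people with no follow-up score.

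In Assessment: state that 3- and 6-month assessments are sought from everyone enrolled whatever their attendance, and report the number assessed at each visit and in each contrast.

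The cost is some SAP wording, slightly more analysis work and staff effort to assess people who stop attending. Estimates may come out smaller, and protection stays partial where both follow-ups are missed for reasons related to response.
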